10.53 Secondary Malignancy

- A **secondary malignancy** is a cancer caused by treatment for a previous malignancy (e.g., treatment with investigational agent/intervention, radiation or chemotherapy). A secondary malignancy is not considered a metastasis of the initial neoplasm.
- All secondary malignancies that occur during the study require reporting to the study team. Three options are available to describe the event:
 - Leukemia secondary to oncology chemotherapy (e.g., Acute Myelocytic Leukemia [AML])
 - Myelodysplastic syndrome (MDS)
 - Treatment-related secondary malignancy

- Any malignancy possibly related to cancer treatment (including AML/MDS) should also be reported via the routine reporting mechanisms outlined in each protocol.

10.54 Second Malignancy

- A second malignancy is one unrelated to the treatment of a prior malignancy (and is NOT a metastasis from the initial malignancy). Second malignancies require ONLY routine reporting.

10.6 Required Routine Reporting

Adverse events to be graded at each evaluation and preintervention symptoms/conditions to be evaluated at baseline per the CTCAE v4.0 grading unless otherwise stated in the table below:

System Organ Class (SOC)	Adverse event/Symptoms	Baseline	Each evaluation
Gastrointestinal disorders	Abdominal pain	X	X
	Bloating	X	X
	Diarrhea		X
	Baseline number of stools per day	X	
	Flatulence	X	X
	Nausea	X	X
	Vomiting	X	X
General disorders and administration site conditions	Fatigue	X	X
Infections and infestations	Wound infection	X	X
Injury, poisoning and procedural complication	Wound complication	X	X
	Wound dehiscence	X	X

10.61 Submit via appropriate MCCC Case Report Forms (i.e., paper or electronic, as applicable) the following AEs experienced by a patient and not specified in Section 10.6

10.611 Grade 2 AEs deemed *possibly, probably, or definitely* related to the study intervention or procedure.

10.612 Grade 3 and 4 AEs regardless of attribution to the study intervention or procedure.

10.613 Grade 5 AEs (Deaths)

10.6131 Any death within 30 days of the patient's last study treatment or procedure regardless of attribution to the study intervention or procedure.

10.6132 Any death more than 30 days after the patient's last study intervention or procedure that is felt to be at least possibly intervention related must also be submitted as a Grade 5 AE, with a CTCAE type and attribution assigned.

11.0 Intervention Evaluation: None**12.0 Descriptive Factors: None****13.0 Follow-up Decision at Evaluation of Participants**

- 13.1 Participants will receive 3 cycles of therapy (12 weeks) with oral SBI or placebo, followed by a 4 week observation visit. No additional follow-up is required for these patients beyond the 4 week observation time point.
- 13.2 Participants who go off the intervention early for unacceptable adverse events or patient refusal of further treatment will go to the observation phase. Patients can continue in the observation phase for total of 16 weeks of study participation.
- 13.3 Participants where post-operative problems occur, study treatment cannot begin, and participant agrees to complete questionnaires will crossover to QOL assessment only. These participants will be followed per the test schedule (Section 4.0).
- 13.4 A participant is deemed *ineligible* if after registration, it is determined that at the time of registration, the participant did not satisfy each and every eligibility criteria for study entry. The patient will go directly off study.
 - If the participant received therapy, all data up until the point of confirmation of ineligibility must be submitted.
 - If the participant never received therapy, on-study material must be submitted.
- 13.5 A participant is deemed a *major violation*, if protocol requirements regarding intervention in cycle 1 of the initial intervention are severely violated that evaluability for primary end point is questionable. All data up until the point of confirmation of a major violation must be submitted. The patient may continue therapy off-protocol at the discretion of the physician as long as there are no safety concerns, and the patient was properly registered.
- 13.6 A participant is deemed a *cancel/withdrawal* if he/she is removed from the study for any reason before any study intervention is given or participant does not agree to crossover to QOL assessment only. On-study material and the End of Active Intervention/Cancel Notification Form must be submitted. No further data submission is necessary.

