2.2 Secondary Efficacy

- 2.21 To compare the surgical complication rates between oral SBI vs. placebo up to 1 month post-surgery (safety endpoint).
- 2.22 To compare the QOL, as derived from the previously-validated Symptom Distress Scale, the PQL (Postoperative Quality of Life questionnaire), and the uniscale (overall QOL item) between patients receiving oral SBI vs. placebo.
- 2.23 To compare the grade 2 or worse adverse event rates for patients receiving oral SBI vs. placebo.
- 2.24 To characterize the adverse event profile of oral SBI in postoperative gynecological cancer patients (safety endpoint).
- 2.25 To compare supplement adherence between patients receiving oral SBI vs. placebo.

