8.0 Dosage Modification Based on Adverse Events

There are no dose modifications in this trial. If the patient experiences a grade 1 or worse adverse event that is thought to be related to the study intervention, the patient should discontinue the intervention and proceed to the 4 week post intervention observation.

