10.3 Assessment of Attribution

When assessing whether an adverse event is related to a medical treatment or procedure, the following attribution categories are utilized:

Definite - The adverse event is *clearly related* to the agent(s).
Probable - The adverse event is *likely related* to the agent(s).
Possible - The adverse event *may be related* to the agent(s).
Unlikely - The adverse event is *doubtfully related* to the agent(s).
Unrelated - The adverse event is *clearly NOT related* to the agent(s).

Events determined to be possibly, probably or definitely attributed to a medical intervention suggest there is evidence to indicate a causal relationship between the agent and the adverse event.

10.4 Expedited Reporting Requirements for Commercial Agent(s) ONLY:

Expedited Reporting Requirements for Adverse Events that Occur in a Non-IND/IDE trial within 30 Days of the Last Administration of a Commercial Agent^{1,2}

ALL SERIOUS adverse events that meet the above criteria **MUST** be immediately reported to the sponsor within the timeframes detailed in the table below.

Hospitalization	Grade 1 Timeframes	Grade 2 Timeframes	Grade 3 Timeframes	Grade 4 & 5 Timeframes
Resulting in Hospitalization ≥ 24 hrs		7 Calendar Days		24-Hour 3 Calendar Days
Not resulting in Hospitalization ≥ 24 hrs	Not required		7 Calendar Days	

NOTE: Protocol specific exceptions to expedited reporting of serious adverse events are found in section 10.41 of the protocol.

Expedited AE reporting timelines are defined as:

- “24-Hour; 3 Calendar Days” - The AE must initially be reported via MedWatch within 24 hours of learning of the AE, followed by a complete expedited report within 3 calendar days of the initial 24-hour report.
- “7 Calendar Days” - A complete expedited report on the AE must be submitted within 7 calendar days of learning of the AE.

¹Serious adverse events that occur more than 30 days after the last administration of investigational agent/intervention and have an attribution of possible, probable, or definite require reporting as follows:

Expedited 24-hour notification followed by complete report within 3 calendar days for:

- All Grade 4, and Grade 5 AEs

Expedited 7 calendar day reports for:

- Grade 2 adverse events resulting in hospitalization or prolongation of hospitalization
- Grade 3 adverse events

Effective Date: May 5, 2011

Additional Instructions:

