15.14 **Administration:** SBI is administered orally or enterally. Each patient will be instructed to add the contents of one packet (5 grams) to a cup and dissolve the powder with approximately on-half cup (4 fl. ounces or 120 mL) of water. The patient will stir to mix and drink the contents. The patient will take one dose twice a day, in the morning and the evening, with or without food. Foods such as applesauce or pudding may be used instead of liquid to blend the product if the patient desires.

15.15 **Potential Agent Interactions:** No significant interactions of SBI with commonly prescribed medications have been observed.

15.16 **Known potential toxicities:** Study subjects with known beef allergies or allergies to other components of SBI should not take SBI. As with any ingested food or product, subjects who develop a hypersensitivity or food intolerance to SBI should discontinue its use. Subjects who are pregnant or breastfeeding should not take SBI, as there are no data regarding the effects. Serum-derived bovine immunoglobulin has self-affirmed generally recognized as safe (GRAS) status, with no objections from the FDA, and is demonstrated to be safe and well tolerated in pediatric and adult patients. SBI is marketed in Mexico, the Czech Republic, Japan, Egypt, and the United States. More than 100,000 kg of SBI in various dosages have been ingested by the general population since 2001. No serious adverse events have been reported to the manufacturer or the FDA. Literature reports indicate AEs include worsening or reoccurrence of diarrhea, constipation, and worsening neuropathy. Increased urination, stomach cramps, fatigue, headache, sore throat, softened stools, and nausea have also been reported.

15.18 Agent procurement:

Serum-derived bovine immunoglobulin protein isolate and matching placebo will be manufactured by Proliant Biologicals, Boone, Iowa in accordance with Good Manufacturing Practice (GMP) and FDA guidelines for medical good ingredients (21 CFR Part 110) and will be provided by Entera Health Inc.

15.19 Nursing Guidelines:

- 15.191 Due to the early investigational nature of this medical food, not all side effects can be known at this time. Assess for side effects and monitor patients closely.
- 15.192 Patients with beef allergy or intolerance should not take SBI.
- 15.193 GI adverse events may occur. Treat symptomatically and monitor for effectiveness.

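### Related grade 1 events end treatment under 8.0, but 10.61 does not require unlisted ones to be submitted, so the SBI adverse event profile (2.24) can omit them, and no section plans related stops by arm

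*Combined protocol and SAP*

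**What the plan says.** Section 8.0 allows no dose modification. It sets a low threshold for stopping: "If the patient experiences a grade 1 or worse adverse event that is thought to be related to the study intervention", the product should be discontinued and the patient moves to the four-week observation period.

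Section 10.6 lists ten symptoms to be graded at every evaluation: six gut symptoms, fatigue and three wound terms. Section 10.61 then covers "the following AEs experienced by a patient and not specified in Section 10.6". For those it asks for grade 2 events that are at least possibly related, "Grade 3 and 4 AEs regardless of attribution to the study intervention or procedure", and deaths within 30 days of the last study treatment (later ones only if possibly related). Grade 1 is not mentioned.

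The expedited-reporting table in 10.4 does not close the gap. In the row "Not resulting in Hospitalization ≥ 24 hrs", grade 1 is marked as not required.

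Section 15.16 names reactions already reported with SBI. It begins with three: "Literature reports indicate AEs include worsening or reoccurrence of diarrhea, constipation, and worsening neuropathy". Its next sentence gives seven more, among them headache, sore throat and a rise in urination. It also says that "subjects who develop a hypersensitivity or food intolerance to SBI should discontinue its use".

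Section 16.61 tabulates the maximum grade of each event type and compares grade 2 or higher rates between arms. Section 16.62 compares compliance categories by arm. Section 16.63 describes QOL in patients who never start or who stop early. None of them names a count of stops for related events by arm.

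**The concern.** The event that ends treatment and the event that must be submitted are defined at different grades. For an unlisted term, a related grade 1 event is enough to take the patient off product but not enough to require a record in the adverse event data. Stopping may also keep the event from ever reaching grade 2, where submission would begin.

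Objective 2.24, labelled a safety endpoint, is to characterize the adverse event profile of SBI. Its source data can omit reactions that the protocol itself treats as sufficient reason to stop, including some it already associates with the product. Section 15.194 has patients told to report any new or worse neuropathy, yet a related grade 1 case that ends product need not be submitted. For a pilot meant to prepare a larger trial, the rate of stopping for related events is a basic tolerability figure, and the plan does not call for it.

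**Working it through.** The plan states no figure on this point, so the check is a cross-reading followed by an illustration of size.

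**Step 1. What a related grade 1 event triggers, without hospitalization**

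| | Listed in 10.6 | Not listed in 10.6 |
|---|---|---|
| Product stopped (8.0) | yes | yes |
| Routine submission (10.6, 10.61) | yes, graded at each evaluation | not required |
| Expedited report (10.4) | not required | not required |
| In the 16.61 frequency tables | yes | only if a site submits it anyway |

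The gap is the right-hand column.

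**Step 2. Which 15.16 reactions fall there**

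Section 15.16 names ten reactions: diarrhea, constipation, neuropathy, increased urination, stomach cramps, fatigue, headache, sore throat, softened stools and nausea. Counting stomach cramps as abdominal pain and softened stools as diarrhea, five are covered by 10.6. The other 10 − 5 = 5 are not: constipation, neuropathy, increased urination, headache and sore throat. Hypersensitivity or food intolerance is also unlisted.

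Constipation differs from the rest. The weekly booklet (Appendix II) asks for bowel movements per day and a Bristol stool type, and 16.63 compares these items between arms. It is therefore partly visible by arm, though without attribution.

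**Step 3. Whether another planned output shows the stops**

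- Compliance (16.62): Appendix V and the Appendix VI phone guide ask how often product was taken, not why it was stopped.
- Phone side effects (Appendix VI): the list repeats the 10.6 terms.
- Early stoppers (16.63): QOL only, with non-starters included, and not separated by cause.
- End of Active Intervention form (18.12): due at the stop. Its fields are not shown and no analysis of it is named.

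**Step 4. Size, for one unlisted term**

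Input from 16.2: 35 evaluable patients per arm, taken here as 35 treated on SBI. The rate r of related grade 1 stops for the term is an assumption; the documents give none.

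Expected cases = 35r. Chance of at least one = 1 − (1 − r)^35.

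| Assumed r | 35r | (1 − r)^35 | Chance of at least one |
|---|---|---|---|
| 1% | 0.35 | 0.703 | 30% |
| 2% | 0.7 | 0.493 | 51% |
| 5% | 1.75 | 0.166 | 83% |
| 10% | 3.5 | 0.02503 | 97% |

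If sites submit only what is required, the table for that term would show none of these cases.

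**Step 5. Precision of a by-arm count of stops**

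Assumed counts: 7/35 on SBI and 2/35 on placebo. The difference is 0.200 − 0.057 = 0.143. Wilson 95% limits are 0.100 to 0.359 and 0.016 to 0.186. Newcombe's interval is then:

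- lower: 0.143 − √[(0.200 − 0.100)² + (0.186 − 0.057)²] = −0.020
- upper: 0.143 + √[(0.359 − 0.200)² + (0.057 − 0.016)²] = 0.307

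So 14 points, with an interval from −2 to 31. A by-arm table supports an estimate only.

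**The case against.** The strongest reply is that the gap is narrow and may be smaller in practice than on paper. The ten 10.6 symptoms are graded at every evaluation, grade 1 included, and they cover the effects most expected of an oral gut product. Section 16.61 tabulates maximum grade by event type, not only grade 2 and above. Section 10.61 sets a minimum, and sites may submit more. At the end of intervention, 18.12 calls for an Adverse Event Form and a Nurse/CRA form as well as the End of Active Intervention form, and any of these may hold the reason for stopping. Section 13.2 already separates unacceptable adverse events from patient refusal. Section 16.6 says the secondary endpoints will be compared between arms and that the monthly call data will be assessed and reported. The rates in the illustration are assumed, and the earlier human studies are described as free of adverse events. The 10% in 16.52 concerns grade 3 or worse events of any type, so it lends no support to a 10% rate for one term.

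Much of this stands. It confines the point to unlisted grade 1 events, makes constipation a weak example, and leaves the size open. It does not remove the point. The frequency tables can hold only what is submitted, and 10.61 decides that for unlisted terms. Section 16.6 is general and names no table of stops. The forms' fields are not shown, and 10.61 still does not require term, grade and attribution for these events.

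A reader might infer that an excess of related stops on SBI would go unreported. The documents do not support that: given 16.6 and the unseen forms, the most that can be said is that it need not be reported.

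**Conclusion.** The point holds in limited form and is worth considering. Following 8.0 and 10.61 exactly, a related grade 1 event outside the 10.6 list can end treatment without being required in the data for objective 2.24, and no section plans related stops by arm. The clear examples are neuropathy, headache, increased urination, sore throat, and hypersensitivity or food intolerance.

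The size is not known. Over the assumed single-term rates of 1% to 10%, between 0.35 and 3.5 cases per 35 treated patients could be left out. This supposes that every case stops at grade 1 and that sites submit only the minimum.

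Two further readings go too far. A reader might infer that grade 1 tolerability is lost altogether; it is not, because the listed terms are captured. A reader might also infer that the efficacy result is compromised; it is not, because the primary endpoint is the PQL total score, analyzed in all eligible, consenting, randomized patients, and does not draw on adverse event submissions.

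**What to change.** In 10.61, add one item: any adverse event of any grade, whether or not listed in 10.6, that leads to stopping product is submitted with term, grade and attribution.

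In 16.61, add one descriptive output: by arm, the number and proportion of treated patients who stopped product for an event thought related, the terms involved, and the difference between arms with its 95% confidence interval. No test is needed.

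The cost is one sentence, one table and slightly more reporting by sites, limited to patients who stop because of an event. If the End of Active Intervention form already records a reason, only term, grade and attribution are new. Sample size, alpha and the primary analysis do not change. The drawback is imprecision at about 35 per arm, so the table should say that finding no difference is not evidence of equal tolerability.

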A large portion of SBI consists of immunoglobulins, primarily IgG and to a lesser extent IgM as well as other proteins and amino acids. SBI is derived from manufacturing processes for bovine serum albumin (BSA), making it a valuable but easily accessible byproduct. Previous studies show that SBI resists part of the digestive process and that some of active IgG remains present in the gastrointestinal tract. This combination of immunoglobulins and other proteins are thought to lead to the immunomodulatory effects of SBI and are thought to lead to maintenance of the intestine as a barrier and attenuation of malabsorption after an inflammatory assault to the gastrointestinal tract. Indeed, when taken together, previous studies show that oral ingestion of SBI improves the absorption of nutrients, reduces intestinal permeability, and decreases overall infection rates. The most striking clinical evidence in support of the above entails the administration of SBI to weanling farm animals with the observation of increased dietary intake and greater weight gain compared to control animals [9-11]. The published literature is replete with observations that show animals maintain their weight during the weaning process and continue to thrive as a result of SBI supplementation.

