We expect about 10% of patients to experience grade 3 or worse adverse events (at least possibly related to the study intervention). In addition, we expect less than 1% of patients to experience a Grade 5 adverse event, at least possibly related to the study intervention. Accrual will be temporarily suspended to this study if at any time we observe adverse events that satisfy any of the following within each arm separately (i.e. if any of the following occur in arm A or arm B, we will suspend accrual to the trial):

- If at any time 4 or more in the first 20 treated patients (or 20% or more after the first 20) experience a Grade 3 or worse adverse event (possibly, probably, or definitely related to the intervention).
- If at any time, 1 patient experiences a grade 5 adverse event (possibly, probably, or definitely related to the intervention).

We note that we will review all Grade 5 adverse events on a case-by-case basis as well (regardless of attribution), and may suspend accrual after just one Grade 5 event, if we feel it is necessary for patient safety.

16.6 Definitions and Analyses of Secondary Endpoints: All these endpoints will be assessed individually and will also be compared between the 2 arms. Monthly phone calls may be used to collect the secondary endpoint information for each patient, including adverse events, surgical complications, and other data (e.g. patient reported weight, intervention compliance, etc.). We will be assessing, reporting on, and potentially analyzing all the data collected from these monthly telephone calls.

16.61 Adverse Events: All eligible patients who have initiated therapy will be considered evaluable for adverse event analyses. The maximum grade for each type of adverse event will be recorded for each patient up to 16 weeks post-randomization (12 weeks of intervention + 1 month post-intervention observation timepoint), and frequency tables will be reviewed to determine adverse event

patterns. The overall adverse event rates for grade 2 or higher adverse events, will be compared using Chi-Square or Fisher's Exact tests. In addition, the surgical complication rates (up to 1 month post-surgery) will also be compared between the 2 arms using Chi-Square or Fisher's Exact tests.

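### The grade 2 or higher adverse event comparison is planned on all causes, but unlisted grade 2 events are required only if judged related, so the rate tested has a mixed definition and is too low

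*Combined protocol and SAP*

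**What the plan says.** Objective 2.23, under Secondary Efficacy, is "To compare the grade 2 or worse adverse event rates for patients receiving oral SBI vs. placebo". Section 16.61 gives the analysis: "The overall adverse event rates for grade 2 or higher adverse events, will be compared using Chi-Square" or Fisher's exact test. It presumes that "The maximum grade for each type of adverse event will be recorded for each patient up to 16 weeks post-randomization". Neither section mentions attribution.

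Section 10.6 sets out what is collected. Its table is headed "Adverse events to be graded at each evaluation and preintervention symptoms/conditions to be evaluated at baseline per the CTCAE v4.0 grading" and lists ten terms for each evaluation: abdominal pain, bloating, diarrhea, flatulence, nausea, vomiting, fatigue, wound infection, wound complication and wound dehiscence. Section 10.61 then covers "the following AEs experienced by a patient and not specified in Section 10.6". For these unlisted terms, 10.611 requires "Grade 2 AEs deemed *possibly, probably, or definitely* related to the study intervention or procedure", while 10.612 requires grade 3 and 4 events whatever their attribution. Deaths follow their own time rule in 10.613.

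**The concern.** The analysis asks for one quantity and the collection rule delivers another. An unlisted grade 2 event judged unlikely to be related, or unrelated, need not appear on the routine forms, yet it belongs in an overall grade 2 or higher rate.

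This bears on the trial's own hypothesis. Section 1.4 says that SBI "decreases overall infection rates", but wound infection is the only infection among the ten listed terms. A prevented infection shows up as fewer unrelated events in the SBI arm, and a filter on relatedness removes such events from both arms before they can be compared.

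There is a safety side as well. Section 15.16 names constipation and worsening neuropathy among reported events, and 15.194 asks nurses to warn of neuropathy. Neither is in the 10.6 table, so at grade 2 both depend on an attribution judgement.

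**Working it through.** **Step 1: what is required, by type of event.**

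| Event | Wanted by 2.23 and 16.61 | Required by 10.6 and 10.61 |
|---|---|---|
| Ten listed terms, grade 2 or higher | any cause | any cause |
| Unlisted, grade 3-4 | any cause | any cause |
| Unlisted, grade 2, judged at least possibly related | yes | yes |
| Unlisted, grade 2, judged unlikely or unrelated | yes | no |

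The last row is the gap.

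**Step 2: do other routes fill it?**

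- Section 10.4 calls for expedited reports of serious grade 2 events that lead to hospitalization, and 10.11 sends expedited events into the routine data. Other hospitalizations during treatment go on a notification form. These routes catch only the hospitalized cases.
- Section 16.6 allows monthly calls but does not require them for this purpose. The side-effect list in the Appendix VI call guide repeats the 10.6 terms and adds none.
- Surgical complications are compared separately, but only to 1 month after surgery. No definition, grading or named form is given for them.

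What remains uncollected is the unlisted, non-hospitalized grade 2 event judged unrelated.

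**Step 3: size, by illustration.** The plan states no adverse event rate or power for this comparison, so there is no figure to reproduce. All rates below are assumptions. The arm sizes are from 16.11 and 16.2 (35 evaluable and at most 50 per arm).

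Let L be the share of patients counted anyway (a listed grade 2 or higher event, or any grade 3-4 event), equal in both arms. Let U be the share with an unlisted grade 2 event, independent of L. Let f be the fraction of the latter called related, taken as equal in both arms because attribution is made blind. Then

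recorded rate = 1 − (1 − L)(1 − fU)

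recorded difference = (1 − L) × f × (U placebo − U SBI)

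The recorded difference is thus f times the true one. Take U = 40% on placebo and 15% on SBI. With L = 30%, the true rates are 1 − 0.7 × 0.6 = 58% and 1 − 0.7 × 0.85 = 40.5%, a difference of 17.5 points. With f = 0.2, the recorded rates are 1 − 0.7 × 0.92 = 35.6% and 1 − 0.7 × 0.97 = 32.1%, a difference of 3.5 points.

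Power below is for Fisher's exact test, two-sided 0.05, by full enumeration at 50 per arm:

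| L | True difference | Recorded, f = 0.5 | Recorded, f = 0.2 | Power, full capture | Power, f = 0.5 | Power, f = 0.2 |
|---|---|---|---|---|---|---|
| 30% | 17.5 points | 8.75 | 3.5 | 36% | 11% | 4% |
| 50% | 12.5 points | 6.25 | 2.5 | 19% | 7% | 4% |
| 70% | 7.5 points | 3.75 | 1.5 | 10% | 5% | 3% |

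At 35 per arm, full-capture power is 21%, 14% and 7%.

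**Step 4: a milder case.** Suppose SBI halves both components (L from 30% or 50%, U from 20% or 40%) and no unlisted grade 2 event is called related. By the normal approximation, power at 35 per arm is 44-72% with full capture and 32-58% with the filter. At 50 per arm it is 58-87% and 43-74%. The loss is then moderate, because the captured events carry much of the effect.

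**The case against.** A reader might infer several stronger things, and the documents do not support them.

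- *The endpoint cannot be computed.* Only the complete all-cause rate is out of reach. A grade 2 or higher rate over the ten listed terms, an all-cause grade 3-4 rate and a related grade 2 or higher rate can all be built from the required data.
- *A fall in infections or bowel complications would be invisible.* Wound infection, wound complication, dehiscence and most gastrointestinal symptoms are graded whatever the cause, and all grade 3-4 events are submitted. The human benefit described in 1.4 is largely less diarrhea and fewer gastrointestinal symptoms, which are mostly listed terms. Bowel function is also reported weekly by patients.
- *Events caused by surgery are lost.* Section 10.611 also admits events related to the procedure. If that means the cancer operation, surgery-attributed grade 2 events are submitted, although those attributed to chemotherapy or to the cancer are still not. Section 10.3 frames attribution around the agent, and the text does not settle the matter.
- *Surgical complications are lost in the same way.* Section 16.6 names them apart from adverse events, and nothing says that they are drawn from the 10.61 forms. The gap there is the missing definition.
- *Power falls from 76% to 6%.* Those figures (40% vs 15% against 8% vs 3%, 50 per arm) are arithmetically right but describe unlisted grade 2 events alone. The planned test is on the overall rate, where Step 3 applies.

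It is also fair to say that this is one secondary comparison in a pilot, and that the Secondary Efficacy heading also covers objectives labelled as safety endpoints. All of these points narrow the concern. None reconciles 10.611 with 2.23 and 16.61.

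**Conclusion.** The mismatch stands. If the plan is followed as written, the grade 2 or higher rate compared between arms will be neither an all-cause rate nor a related-only rate. It will understate the all-cause rate and largely miss differences in unlisted, non-hospitalized grade 2 events judged unrelated. Listed wound and gastrointestinal events and all grade 3-4 events remain captured.

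That conclusion rests on the text alone. The size rests on assumed rates and ranges from a moderate loss, where SBI also reduces the captured events, to near-complete loss of the difference, where its effect lies in unlisted events that few would call related. In the latter case the test would be weak even with full capture (36-10% at 50 per arm). The reason to change the plan is therefore to obtain an interpretable, unfiltered estimate for the larger study that this pilot is meant to inform, rather than to gain power. Events not recorded during the trial are hard to recover later.

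**What to change.** Preferred: change 10.611 to require grade 2 events regardless of attribution, with attribution still recorded, over the 16 weeks used in 16.61. Run the 2.23 comparison on all-cause events and give related-only events as a secondary table. The cost is a wording change and more lines on the existing Adverse Event Form, for at most 100 patients, at contacts already scheduled.

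Otherwise: leave collection as it is and restate 2.23 and 16.61 as two comparisons, (i) grade 2 or higher for the ten listed terms and (ii) grade 3 or higher for all terms. This costs only wording, but gives up the unlisted grade 2 events.

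In either case, state whether the procedure in 10.611 includes the cancer surgery, and define a surgical complication and the form on which it is recorded.
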